17.6 ITT and Per-Protocol Analyses, Missing Data and Dropouts

Analysis will be ITT in the sense that patients will be analyzed as being members of the arm to which they were originally randomized. We plan no special adjustments for missing data.

17.7 Interim Analysis

No interim analysis is contemplated.

17.8 Safety Analysis

Adverse events (AEs), including serious adverse events (SAEs), will be summarized by body system and preferred term using MedDRA (The Medical Dictionary for Regulatory Activities). Adverse events will be presented in two ways: (1) the number and proportion of participants experiencing at least one incidence of each event will be presented overall and by treatment group; and (2) a table displaying the total number of each event will be given overall and by treatment group. Listings of serious adverse events will be given, sorted by treatment, body system, and preferred term. Detail in these listings will include severity, relationship to study drug, and action taken as available. Treatment arm differences will be monitored by the DSMB.

18.0 REGULATORY COMPLIANCE AND SAFETY

18.1 Regulatory Compliance

Prior to local study initiation, site investigators will obtain written IRB approval to conduct the study at their respective sites. When changes to the study protocol become necessary, amendments will be submitted in writing by the investigators for IRB approval prior to implementation. In addition, local IRBs will approve all consent forms, recruitment materials, and any materials given to the participant. Annual reports and progress reports will be submitted to the IRBs yearly or at a frequency requested by each IRB. Each site investigator is responsible for maintaining research files that include copies of IRB-approved consent documents and all IRB/IEC (Institutional Ethics Committee) approval memos for Initial and Continuing/Annual Reviews, protocol modifications, and any other modification made in the course of the study. All initial approval documents (approval memos and informed consents) must be provided to the lead team investigator prior to the initiation of research activities at a given site and all regulatory documents must be available at any time for an audit.

18.2 Statement of Compliance

This trial will be conducted in compliance with the current version of the protocol, current Good Clinical Practice (GCP), the principles of the Declaration of Helsinki, and all other applicable regulatory requirements. Participating sites must obtain written approval of the study protocol, informed consent form, other supporting documents, and any advertising for participant recruitment from their local institutional review board (IRB) in order to participate in the study. Prior to study initiation, the protocol and the informed consent documents will be reviewed and approved by an appropriate Ethics Review Committee (ERC) or IRB. Any amendments to the protocol or consent materials must be approved before they are implemented. Annual progress reports and local Serious Adverse Event (SAE) reports will be submitted to each IRB, according to its usual procedures.

18.3 Confidentiality

By signing the protocol signature page, the investigator affirms that information furnished to the investigator by NIDA will be maintained in confidence and such information will be divulged to the IRB, Ethical Review Committee, or similar expert committee; affiliated institution; and employees only under an appropriate understanding of confidentiality with that board or committee, affiliated institution and employees. The Lead Investigator will obtain a federal Certificate of Confidentiality (CoC) protecting participants against disclosure of sensitive information (e.g., drug use) and will distribute it to all sites when received. The NIH office that issues the CoC will be advised of changes in the CoC application information. Participating CTP sites will be notified if CoC revision is necessary.

Participant records will be kept confidential by the use of study codes for identifying participants on CRFs, secure and separate storage of any documents that have participant identifiers, and secure computer procedures for entering and transferring electronic data.

18.4 Health Insurance Portability Accountability Act (HIPAA)

Study sites may be required by their institutions to obtain authorization from participants for use of protected health information. Sites will be responsible for communicating with their IRBs or Privacy Boards and obtaining the appropriate approvals or waivers to be in regulatory compliance.

18.5 Investigator Assurances

Each CTP (community treatment program) and their respective IRB that will be reviewing the study must have on record a Federal Wide Assurance (FWA) with the DHHS Office of Human Research Protection. This sets forth the commitment of the organization (CTP or IRB) to establish appropriate policies and procedures for the protection of human research subjects, with documentation to be sent to NIDA or its designee. Research covered by these regulations cannot proceed in any manner prior to NIDA's receipt of certification that the research has been reviewed and approved by the IRB provided for in the assurance (45 CFR 46.103(b) and (f)). Prior to initiating the study, the principal investigator and sub-investigators at each study site will sign a protocol signature page, providing assurances that the study will be performed according to the standards stipulated therein.

18.6 Financial Disclosure

All investigators will comply with the requirements of 42 CFR Part 50, Subpart F to ensure that the design, conduct, and reporting of the research will not be biased by any conflicting financial interest. It is the responsibility of the investigator and the entire local research team to maintain appropriate disclosure to their individual institution according to their requirements.

18.7 DEA Registration

XR-NTX is not a controlled substance. No DEA registration is required for facilities to receive, prescribe or dispense study drug.

18.8 Drug Accountability

Upon receipt, the investigator, pharmacist, or authorized designee at each site is responsible for taking inventory of the investigational agents. A record of this inventory must be kept and usage must be documented. Any unused or expired investigational agent must be accounted for.

18.9 Inclusion of Women and Minorities

Unless specified in the eligibility criteria, the study enrollment is open to any gender, race, or ethnicity. A diverse group of study sites will be involved so that the study can enroll a diverse study population. If difficulties are encountered in recruiting an adequate number of women and/or minorities, these will be discussed in national conference calls and face-to-face meetings, encouraging such strategies as linkages with medical sites and/or treatment programs that serve a large number of women or minorities or advertising in newspapers or radio stations with a high female or minority audience.

18.10 IND Requirements

Medications to be used in this study will be used in accordance with their approved labeling and therefore there is no plan to submit an IND application.

18.11 Regulatory Files

The regulatory files should contain all required regulatory documents, study-specific documents, and all important communications. Regulatory files will be available at each participating site for inspection and compliance monitoring prior to study initiation, throughout the study, and at study closure.

18.12 Records Retention and Requirements

Research records for all study participants (e.g., case report forms, source documents, signed consent forms, and regulatory files) are to be maintained by the investigator in a secure location for a minimum of 3 years after the study is complete and closed. These records are also to be maintained in compliance with local IRB, state, and federal requirements, whichever is longest. In the case of HIPAA-protected records, this time length is six years. The sponsor and lead investigator must be notified in writing and acknowledgment must be received by the site prior to the destruction or relocation of research records.

18.13 Audits

The sponsor has an obligation to ensure that this trial is conducted according to good research practice guidelines and may perform periodic quality assurance audits for protocol compliance. The Lead Investigator and authorized staff from the National Lead Study Team; the National Institute on Drug Abuse Clinical Trials Network (NIDA CTN, the study sponsor); NIDA's contracted agents, monitors, or auditors; and other agencies such as the Department of Health and Human Services (DHHS), the Office for Human Research Protection (OHRP) and the sites Institutional Review Board may inspect research records for verification of data, compliance with federal guidelines on human participant research, and to assess participant safety.

18.14 Reporting to Sponsor

The site principal investigator agrees to submit accurate, complete, legible and timely reports to the Sponsor, as required. These include, but are not limited to, reports of any changes that significantly affect the conduct or outcome of the trial or increase risk to study participants. Adverse Event and Serious Adverse Event reporting will occur as described in Appendix A - Adverse Event Reporting Definitions and Procedures. At the completion of the trial, the national Lead Investigator will provide a final report to the Sponsor.

18.15 Informed Consent

The informed consent process is a means of providing study information to each prospective participant and allows for an informed decision about participation in the study. All potential candidates for the study will be given a current local IRB-approved copy of the Informed Consent Form to read. Appropriately qualified and trained study personnel will explain all aspects of the study in lay language and answer all of the study candidate's questions. Participants who remain interested after receiving an explanation of the study will be given an informed consent quiz to test his/her understanding of the trial, the purpose and procedures involved, and the voluntary nature of his/her participation. Those who cannot successfully answer the quiz questions will have the study re-explained by research staff with a focus on those aspects they did not understand. Anyone who cannot demonstrate appropriate understanding of the study will be ineligible to participate and will be assisted in finding other treatment resources. Those who demonstrate understanding of the study and voluntarily agree to participate will be asked to sign the Informed Consent Form. Participants will not be administered any assessments or study procedures prior to signing the informed consent.

For this study, there will be two consents, one for pre-screening and one for trial consent. Both consents are to be treated equally in terms of regulatory and protocol requirements (e.g., approved by Lead Team and local IRB before site initiation, signed and dated by participant, etc.).

Each study site must have the pre-screening and trial consents approved by their local IRBs. A copy of the IRB-approved consents, along with the IRB study approval, must be sent to the Clinical Coordinating Center

(CCC) and the Lead Node prior to the site initiation visit and with each subsequent consent revision. The Informed Consent Form must be updated or revised whenever important new safety information is available or whenever the protocol is amended in a way that may affect a study participant's participation in the trial. The site must maintain the original and signed Informed Consent Form for each participant in a locked and secure location that is in compliance with their local IRB and institutional policies. The consent forms must also be accessible for quality assurance review and regulatory compliance. Every study participant should be given a copy of the signed document to keep for their reference. Individuals who refuse to participate or who withdraw from the study will be treated without prejudice.

18.16 Clinical Monitoring

Monitoring of the study site will be conducted on a regular basis using a combination of NIDA- contracted monitors and Node Quality Assurance (QA) staff. Investigators will host periodic visits by both the NIDA-contracted monitors and local site managers; the purpose of which is to encourage and assess compliance with GCP requirements and to document the integrity of the trial progress. The national and local monitors will audit the following items, but not exclusively: regulatory documents, case report forms, Informed Consent Forms, and any corresponding source documents for every participant. Monitors will have the opportunity and ability to review any study-associated document or file.

NIDA-contracted monitors will assess whether submitted data are accurate and in agreement with source documentation and will also review regulatory/essential documents such as correspondence with the IRB. Areas of particular concern will be participant Informed Consent Forms, protocol adherence, reported safety events and corresponding assessments, study drug accountability, and principal investigator oversight and involvement in the trial. Reports will be prepared following the visit and forwarded to the site principal investigator, the lead investigator and NIDA CCTN.

Qualified node personnel will provide site management and monitoring for each site during the trial. This will take place as specified by the local protocol team, node PI, or lead team and will occur as often as needed to help prevent, detect, and correct problems at the study sites. Node (QA) staff will audit source documentation, including all Informed Consent and HIPAA forms (if applicable). Node QA staff will verify that study procedures are being properly followed and that site staff is trained and able to conduct the protocol appropriately. If the node QA staff's review of study documentation indicates that additional training of study personnel is needed node QA staff will undertake or arrange for that training. Details of the contract, Node QA, and data monitoring are found in the study monitoring plan.

18.17 Study Documentation

Study documentation includes all case report forms, workbooks, source documents, monitoring logs and appointment schedules, sponsor-investigator correspondence, signed protocol and amendments, Ethics Review Committee or Institutional Review Board correspondence and approved current and previous consent forms and signed participant consent forms.

Source documents include all recordings of observations or notations of clinical activities and all reports and records necessary for the evaluation and reconstruction of the clinical research study. The original recording of an observation should be retained as the source document. If the original recording of an observation is the electronic record, that will be considered the source.

19.0 SAFETY MONITORING

19.1 Data and Safety Monitoring Board (DSMB)

This study will utilize the CTN DSMB to oversee ongoing trial progress to assure protection of participants' safety while maintaining that the study's scientific goals are being met. The CTN DSMB is responsible for conducting periodic reviews of accumulating safety and efficacy data. It will determine whether there is support for continuation of the trial, evidence that study procedures should be changed, or if the trial should be halted (for safety, efficacy, or recruitment or performance reasons). This process is intended to assure the IRBs, sponsor, and investigators that participants are provided with an accurate and ongoing risk evaluation when participating in CTN research trials.

Monitoring will begin with the initial review of the protocol during the study development process and continue throughout the study with meetings at least annually. Recommendations and reports from these reviews will be distributed to the site lead investigator for submission to their IRB.

19.2 Protocol Deviations Reporting and Management

Any departure from procedures or requirements outlined in the protocol will be classified as protocol deviations. A protocol deviation is an action (or inaction) that alone may or may not affect the scientific soundness of the investigation or seriously affect the safety, rights, or welfare of a study participant. In some cases, a protocol deviation may compromise participant safety, participant rights, inclusion/exclusion criteria or the integrity of study data and is cause for corrective action to resolve the departure and to prevent re-occurrence. Protocol deviations will be monitored at each site for (1) significance, (2) frequency, and (3) impact on the study objectives, to ensure that site performance does not compromise the integrity of the trial. The decision about whether a deviation from the protocol will be designated as minor or major will be made by the Clinical Coordinating Center (CCC) in conjunction with the protocol's Lead Investigator(s). The consequences will be specified and participating sites will be informed.

All protocol deviations will be recorded in the Electronic Data Capture (EDC) system via the Protocol Deviation CRF. The CCC, DSC and the Lead Investigator must be contacted immediately if an unqualified or ineligible participant is randomized into the study.

Additionally, each site is responsible for reviewing their local IRB's definition of a protocol deviation or violation and understanding which events need to be reported. Sites must recognize that the CTN and IRB definition of a reportable event may differ and act accordingly in following all reporting requirements for both entities.

19.3 Adverse Events (AEs)

The Lead Investigator may appoint a Study Clinician (MD, DO, NP or PA) for this study, who will review or provide consultation for each serious event as needed. These reviews will include an assessment of the severity and causality of the event to the study intervention (drug or therapy) or other study procedures. The Study Clinician will also provide advice for decisions to exclude, refer, or withdraw participants as required. In addition, NIDA will assign a centralized Medical Monitor to this protocol to independently review the safety data, present it to the DSMB for periodic review, and provide PIs a Safety Letter when necessary for submission to IRBs for regulatory compliance. The medical monitor will determine which safety events require expedited reporting to NIDA, the DSMB, pharmaceutical/distributors, and regulatory authorities. This will include events that are serious, related, and unexpected. The study staff will be trained to monitor for and report Adverse Events and Serious Adverse Events.

19.3.1 Adverse Events

For the purposes of this study, all Adverse Events will require reporting in the data system.

19.3.2 Serious Adverse Events:

For the purpose of this study, the following events will not be reported as an SAE, but will be recorded on study specific forms in the data system. They would be reported to local IRBs per local IRB guidelines:

- 1) Detox admissions (documented instead on the DTX form).
- 2) Admission for labor and delivery.
- 3) Admission for elective or pre-planned surgery.

19.4 Known Potential Toxicities of Study Drug/Intervention

Refer to the package insert for XR-NTX.

19.5 Known Potential Adverse Events Related to the Underlying Clinical Condition and/or Study Populations

Each of the participating research sites have established practices for managing medical and psychiatric emergencies, and the study staff will continue to utilize these procedures. Treatment providers at each research site will be responsible for monitoring participants for possible clinical deterioration or other problems, and for implementing appropriate courses of action.

As this population will have significant ongoing health and substance use issues, events related to complications of HIV, substance use treatment or admission for substance detoxification, hospitalizations for medical and psychological reasons and deaths will be captured on study specific forms and not duplicate reported as an adverse or serious adverse event. These data will still be included in the reports to the DSMB at the regular meetings.

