15.3 Fatal Overdose

We will collect data on fatal overdoses using medical chart record review at 16 weeks for participants who are lost to follow-up. We will supplement this with information from contacts with persons listed on the participant's locator form when participants are lost to follow-up throughout the study. If a fatal overdose occurred, the event also should be captured on the AE/SAE CRF.

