22.4 Site's Role in Eliciting and Reporting Adverse Events

Appropriately qualified and trained study staff will elicit participant reporting of AEs and SAEs at each study visit designated to collect AEs. Adverse events (medical and/or psychiatric) assessment will initiate with participant consent and follow-up will continue through 30 days post last study visit. Study staff will obtain as much information as possible about the reported AE/SAE to complete the AE/SAE forms and will consult as warranted.

Standard reporting, within 7 days of the site becoming aware of the event, is required for reportable AEs. Expedited reporting (within 24 hours of their occurrence and/or site's knowledge of the event) is required for reportable SAEs (including death and life-threatening events). Local sites are responsible for reporting SAEs to their IRB, per their IRB's guidelines.

Site staff is required to enter reportable AEs and SAEs in the AdvantageEDC system. The AE form is used to capture reportable AEs (as defined in the protocol). Additional information may need to be gathered to evaluate serious adverse events and to complete the appropriate CRFs and the summary. This process may include obtaining hospital discharge reports, medical records, autopsy records or any other type records or information necessary to provide a complete and clear picture of the serious event and events preceding and following the event. If the SAE is not resolved or stable at the time of the initial report or if new information becomes available after the initial report, follow-up information must be submitted as soon as possible.

Reportable adverse events will be followed until resolution, stabilization or study end. Any serious adverse reactions will be followed until resolution or stabilization even beyond the end of the study.

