22.6.3 Sponsor's Role in Safety Management Procedures of AEs/SAEs

A NIDA-assigned Medical Monitor is responsible for reviewing all serious adverse event reports. All reported SAEs will generate an e-mail notification to the Medical Monitor, Lead Investigator, and designees. All SAEs will be reviewed by the Medical Monitor in AdvantageEDC and, if needed, additional information will be requested. The medical monitor will also report events to the sponsor and the Data and Safety Monitoring Board (DSMB). The DSMB will receive summary reports of all adverse events annually, at a minimum. The DSMB or the NIDA assigned Medical Monitor may also request additional and updated information. Details regarding specific adverse events, their treatment and resolution, will be summarized by the medical monitor in writing for review by the sponsor and DSMB. Subsequent review by the Medical Monitor, DSMB, FDA and ethics review committee or IRB, the sponsor, or relevant local regulatory authorities may also suspend further trial treatment at a site. The study sponsor, DSMB and FDA retain the authority to suspend additional enrollment and treatments for the entire study as applicable.

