22.10 Adverse Event Reporting Chart

23.0 APPENDIX B

DATA SAFETY AND MONITORING PLAN (DSMP)

Brief Study Overview

The primary goal of the CTN-0055 study is to compare HIV viral suppression (HIV-1 RNA < 200 copies / ml at 6 months) among study participants randomized to XR-NTX vs those randomized to office-based BUP/NX. Secondary aims are to compare the effectiveness of XR-NTX vs BUP/NX in 1) HIV outcomes 2) engagement in HIV care 3) change in substance use, 4) change in HIV risk behaviors, 5) change in health related quality of life, and 6) participant safety. Details for the definitions and reporting of safety events are found in the protocol (Appendix A).

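### Section 19.5 takes deaths and medical or psychiatric admissions out of AE/SAE reporting, while 15.3, 19.3.2 and Appendix A require them in it

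*Protocol*

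**What the plan says.** Section 19.5 covers events tied to the underlying condition and the study population. It groups HIV complications, substance use treatment and detoxification admissions with other admissions and deaths. Its words on the last two are that "hospitalizations for medical and psychological reasons and deaths will be captured on study specific forms and not duplicate reported", and the whole group is to be "captured on study specific forms and not duplicate reported as an adverse or serious adverse event". It adds: "These data will still be included in the reports to the DSMB at the regular meetings".

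Other sections set different rules:

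- Section 15.3: "If a fatal overdose occurred, the event also should be captured on the AE/SAE CRF". Section 15.2 has a parallel rule for a non-fatal overdose that leads to an adverse event.
- Section 19.3.1 requires every adverse event to be entered in the data system.
- Section 19.3.2: "the following events will not be reported as an SAE, but will be recorded on study specific forms in the data system". Three items follow: detoxification admissions, admissions for labor and delivery, and elective or pre-planned surgery.
- Section 22.1 (Appendix A) makes death and inpatient hospitalization criteria for seriousness, and requires a death to be reported whatever its cause.
- Section 22.4 (Appendix A) says that expedited reporting, within 24 hours, "is required for reportable SAEs (including death and life-threatening events". Section 23.1.1 (Appendix B) repeats this.

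**The concern.** The protocol gives two instructions for the same events and does not clearly say which prevails. The choice affects more than where a form is filed, because the AE/SAE record is the entry point for safety oversight and for the arm comparison. Section 22.6.3 says: "All reported SAEs will generate an e-mail notification to the Medical Monitor, Lead Investigator, and designees". Under 23.1.2 the Medical Monitor reviews SAEs when they are entered. Under 22.8 the DSMB hears of expedited SAE reports between meetings. The tables and listings by treatment group in 17.8 are built from AEs and SAEs. An event kept off the AE/SAE form has no stated route into any of these.

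This trial follows overdose, liver toxicity and suicidality as safety matters, and each can present as an admission or a death. It has two sites and at most 50 participants, so a difference in reporting between sites, or a handful of diverted events, could change the by-arm safety picture.

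**Working it through.** No formula applies. The check sets the rules side by side for each kind of event, then follows what depends on the answer.

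| Event | 19.5, read literally | Other sections | Agree? |
|---|---|---|---|
| Detoxification admission | Not an AE/SAE; own form | 19.3.2: exempt from SAE reporting; own form | Yes |
| Labor and delivery; planned surgery | Admission, so not an AE/SAE | 19.3.2: exempt from SAE reporting | Yes, on SAE status |
| Unplanned medical or psychiatric admission | Not an AE/SAE | 22.1: serious; not among the three exemptions in 19.3.2 | No |
| Fatal overdose | A death, so not an AE/SAE | 15.3: also on the AE/SAE form; 22.1 and 22.4: reported, within 24 hours | No |
| Death from another cause | Not an AE/SAE | 22.1: reported whatever the cause; 22.4 and 23.1.1: within 24 hours | No |

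The conflicts with 15.3, 22.1 and 22.4 are explicit. The conflict with 19.3.2 is one of scope: its list is closed and contains neither deaths nor unplanned admissions.

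**Does any text settle which rule prevails?** Section 18.14 defers AE and SAE reporting to Appendix A, which favors the 24-hour rule. But 22.4 in Appendix A limits that rule to reportable events and refers back to the protocol for what is reportable. Section 19.5 is part of that protocol. The cross-references run in both directions, so they set no clear order. The word reportable does not rescue 19.5 either, because the same sentence in 22.4 names death as included.

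**What follows if a site obeys 19.5?**

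1. No SAE is entered, so the e-mail of 22.6.3 is not sent and the review on entry in 23.1.2 does not start.
2. There is no expedited SAE report for the DSMB under 22.8. What remains is the regular meeting promised in 19.5.
3. The event is absent from the AE/SAE tables and listings of 17.8.

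**Timing.** The SAE route has a limit of 24 hours. The 19.5 route depends on DSMB meetings, which 19.1 sets at least annually. The pilot lasts at most 12 + 5 = 17 months. Since 17/12 is about 1.4, the annual minimum alone guarantees only one meeting in that span. More may be held.

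**The case against.** The best case for the plan is that 19.5 was meant only to prevent double entry. It gives a reason, namely that this population has substantial continuing health and substance use problems. It keeps the data in DSMB reports, and its heading may confine it to events arising from the underlying condition. On that reading a suspected drug reaction leading to admission would still be an SAE. Section 18.14 points to Appendix A, the annual meeting is a floor, 22.8 lets the DSMB ask for more frequent reports, and 19.3 has the Medical Monitor independently review safety data.

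Much of this stands, and it limits what can be claimed:

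- A reader might infer that the SAE table would be nearly empty. The protocol gives no rate of deaths or admissions, so nothing supports that. Overdoses also have their own rule in 15.2 and 15.3 and their own analysis in 17.5.
- A reader might infer that 19.5 deletes seriousness criteria. The criteria in 22.1 are unchanged; the conflict is over whether events that meet them are reported.
- A reader might infer that sites have nowhere to record these events, because the CRF table in 10.1 shows no general hospitalization form and no all-cause death form. That table is not exhaustive: the end-of-medication form of 11.7 has no row of its own. The reporting chart in 22.10 also cannot be seen in the copy reviewed.
- A reader might infer that the data are lost. Section 19.5 says that they are recorded and reach the DSMB.

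None of this removes the contradiction. Avoiding double entry is exactly what 15.3 declines to do for fatal overdose. Section 22.1 requires deaths to be reported regardless of cause, so limiting 19.5 to condition-related deaths does not reconcile the two.

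**Conclusion.** The protocol contradicts itself on whether deaths and unplanned admissions enter AE/SAE reporting. A site that follows 19.5 as written could bypass 24-hour reporting, the Medical Monitor alert, expedited DSMB notice and the by-arm outputs of 17.8. The effect is a possibility rather than an established outcome: it depends on which section a site follows and, for admissions, on how widely it reads the heading of 19.5. Its size in events cannot be stated from the protocol. The change in timing can be: from 24 hours to the next regular DSMB meeting. Because the rule governs the reporting of deaths and is cheap to repair, it should be settled in the text and not left to site judgment.

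The Appendix B overview is a separate defect. It says "The primary goal of the CTN-0055 study is to compare HIV viral suppression (HIV-1 RNA < 200 copies / ml at 6 months" and names office-based BUP/NX as the comparator. This pilot compares XR-NTX with TAU over 16 weeks, with initiation and retention as its randomized primary outcomes. That mismatch neither causes nor worsens the reporting conflict; the operative text in 23.1.1 in fact supports 24-hour reporting.

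**What to change.** 1. In 19.5, remove deaths and all hospitalizations outside the 19.3.2 list from the exemption. State one rule: these events go on the AE/SAE form within the 24-hour limit of 22.4 and 23.1.1 and into the outputs of 17.8.
2. If the sponsor keeps an exemption for condition-related events, such as HIV complications that are neither fatal nor lead to a non-exempt admission, list it in identical terms in 19.3.2 and 19.5, bring 19.3.1 into line, and tabulate the exempt events by arm. Removing HIV complications altogether is not needed to cure the conflict over deaths and admissions.
3. Check that 15.2, 15.3, 18.14 and the chart in 22.10 agree with the rule adopted.
4. Separately, rewrite the Appendix B overview to give this pilot's comparator, outcomes and 16-week duration.

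The cost is a text amendment, a note to the two sites and some additional SAE forms in a trial of at most 50 participants. The design, sample size and primary analysis do not change.
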